#### 11.1.6 Secondary Effectiveness Endpoint: Mean Metabolic-Chronotropic Relation (MCR) Slope from the Kay-Wilkoff Model at the 3 Month Visit

The Secondary Effectiveness Endpoint evaluates the adequacy of the EMPOWER PG Rate Response feature using the Metabolic-Chronotropic Relation Slope (MCR Slope). Data for this endpoint will be obtained from the subset of subjects who performed treadmill testing at 3 months. Using the Kay-Wilkoff model, the Secondary Effectiveness Endpoint will evaluate the proportionality of the EMPOWER PG's sensor-indicated rate to the subject's workload during the treadmill test. In order to control the overall study Type I error rate, this endpoint will only be evaluated if Safety Endpoint 1 and the primary effectiveness endpoints are successful.

#### 11.1.6.1 Hypotheses

The following set of hypotheses will be used to evaluate the Secondary Effectiveness Endpoint:

H0: Mean slope < 0.65 or Mean slope > 1.35

HA:  $0.65 \le$  Mean slope  $\le 1.35$ ,

where the mean slope is calculated from the Kay-Wilkoff model.

#### 11.1.6.2 Sample Size

A minimum of 35 usable datasets is required to sufficiently power the Secondary Effectiveness Endpoint. A usable dataset is defined as one for which the subject completes at least treadmill Stage 4 without continuous use of the treadmill handlebars in either treadmill Stage 3 or Stage 4, as described further in Document 92614291 (provided separately).

Sample size estimates were obtained using two one-sided t-tests (TOST).

The sample size of 35 usable datasets was calculated using the following assumptions:

- Performance goals = mean slope between 0.65 and 1.35
- Expected standard deviation = 0.35
- One-sided significance level = 2.5%
- Power = 90%

Assuming that 40% of subjects will not have usable datasets, at least 59 subjects will be included in the treadmill test in order to obtain at least 35 usable datasets.

The sample size for this study was not determined by this endpoint.

#### 11.1.6.3 Statistical Methods

All datasets from treadmill tests at 3 months with at least 4 stages of data will be included in the endpoint evaluation. Normalized sensor-indicated rate and normalized workload (METS) will be used for evaluation; the range of values for each normalized value will be between 0 and 1. The normalized rates will be calculated as follows:

 $\begin{aligned} \text{Normalized sensor rate} &= \frac{(\text{sensor rate}_{stage} - \text{sensor rate}_{rest})}{(\text{sensor rate}_{max} - \text{sensor rate}_{rest})} \\ \text{where sensor rate}_{rest} &= \text{Programmed LRL during treadmill test} \\ \text{Normalized workload} &= \frac{(\text{METS}_{stage} - 1)}{(\text{METS}_{max} - 1)} \end{aligned}$ 

Subject-specific slopes from each test will be calculated by performing a general linear model with normalized sensor rate as the outcome and normalized workload as the predictor. These subject-specific slopes will be used in a TOST using an alpha of 2.5% for each test. If the lower limit of the 95% confidence interval is greater than 0.65 and the upper limit of the 95% confidence interval is less than 1.35, then the null hypothesis will be rejected. Each comparison represents a one-sided 2.5% test. Per Union-Intersection Test methodology, the overall alpha is maintained at 2.5%.

#### 11.2 Ancillary Objectives

The following data will be collected in the MODULAR ATP Clinical Study and summarized at the time of endpoint analysis for all subjects, where applicable, and the data are available. Additional information regarding the ancillary objectives can be found in the MODULAR ATP SAP.

- Summary of the mCRM Therapy System implant procedure characteristics
  - o Initial implant success rate of the EMPOWER PG
  - o Initial implant success rate of the S-ICD (de novo Implants)
- Summary of pacing impedance and sensing amplitude at protocol-required follow ups
- Summary of ventricular tachycardia (VT)/ ventricular fibrillation (VF) conversion and sensing interaction testing
- Summary of Communication Threshold Test at Implant, Pre-Discharge, 1 Month Visit and available Semi-Annual visits
- Summary of Communication Test results at available Semi-Annual visits
- Summary of incidence and threshold for Communication Muscle Stimulation at Implant
- Summary of number of postures with a successful Communication Test at the 6 Month Visit
- Summary of EMPOWER PG PCT at protocol-required follow ups
- Summary of spontaneous treated VT/ VF episodes
- Incidence of syncope related to treated and untreated spontaneous episodes of VT/ VF above the lowest programmed rate cutoff
- Incidence and appropriateness of post-shock demand pacing by the EMPOWER PG

- Summary of Inappropriate Therapy
- Summary of Major EMPOWER MPS System- and Procedure-related Complications through both 6 and 12 months after the implant procedure
- Summary of mCRM Therapy System-related complications through both 6 and 12 months after the implant procedure\*
- Summary of the EMPOWER PG performance from Holter Monitor recording
- Summary of EMPOWER PG battery charge remaining to End of Service (EOS) at protocol-required follow ups
- Summary of S-ICD PG remaining battery to Elective Replacement Indicator (ERI) per protocol-required follow ups (baseline adjusted to time of enrollment for S-ICD PGs implanted prior to enrollment in MODULAR ATP)

#### 11.4 Sample Size Summary

The study will enroll up to 300 subjects, which is approximately what is required for the sample size of the final analysis of Safety Endpoint 1, 223 subjects followed for 6 months or 298 subjects enrolled and accounting for an estimated 25% attrition rate ( $223 \approx 298 \times 75\%$ ).

# 11.5 General Statistical Methods

# 11.5.1 Study Success Criteria and Control of Type I Error

The study will be considered successful if Safety Endpoint 1 and all primary effectiveness endpoints are passed.

Safety Endpoint 1 and the primary effectiveness endpoints can be tested at the significance level of 2.5% while still maintaining the overall type I error level at no greater than 2.5%. This follows the methodology of the Intersection-Union Test (IUT). Additionally, in order to control the overall type I error level a gating approach will be employed. The Secondary Effectiveness Endpoint and Secondary Safety Endpoint will only be evaluated if Safety Endpoint 1 and the primary effectiveness endpoints are successful. The secondary endpoints will be tested in the following order:

- Secondary Effectiveness Endpoint
- Secondary Safety Endpoint, which will only be tested if Seconardy Effectiveness Endpoint is successful.

#### 11.5.2 Control of Systematic Error/Bias

Selection of patients will be made from the Investigator's usual patient population. All patients meeting the eligibility criteria and having signed the ICF will be eligible for enrollment in the study. To control for inter-observer variability among sites, an independent CEC will determine the EMPOWER MPS System- and Procedure-related complications to be used in the analysis of Safety Endpoint 1.Number of Subjects per Study Site

To avoid any study site effect and bias, no study site will be authorized to implant or attempt more than 20% of the maximum number of subjects without approval from BSC. A minimum of 50% of total enrollments from North America will be maintained.

# 11.6 Data Analyses

#### 11.6.1 Interim Analyses

# 11.6.1.2 Endpoints

As stated in **Section 11.3** the single interim endpoint analysis will occur after a minimum of 134 subjects who have undergone an EMPOWER PG implant procedure have been followed for 6 months. The final analysis of this endpoint may occur when 223 subjects who have undergone an EMPOWER PG implant procedure have been followed for 6 months if the null hypothesis of Safety Endpoint 1 is not rejected at the interim analysis. The hypothesis test for Primary Effectiveness Endpoints 1 and 2 and the Secondary Effectiveness Endpoint will be performed in conjunction with either the interim analysis of Safety Endpoint 1 if the null hypothesis is successfully rejected or at the time of final analysis if it is necessary.

# **11.6.2 Subgroup Analyses**

Analyses will be performed for each endpoint to determine whether significant differences exist in endpoint results between subgroups. The list of subgroups (with applicable definitions in parentheses) includes, but is not necessarily limited to:

- Sex (Female vs. Male),
- BMI (Obese BMI ≥ 30 vs. Non-Obese BMI < 30) for effectiveness endpoints only,
- Geography (North America vs. Other Countries),
- Age (< 65 years vs.  $\geq$  65 years),
- Race (Black or African heritage vs. other races)

The subgroup variable will be added to a logistic regression model. A test for significance at the 15% level will be performed. For each subgroup variable in which a significant difference exists, the results for each subgroup will be presented separately. BSC does not plan to seek labeling for these subgroups based on these analyses.

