#### 11.1.1.2 Sample Size

A group sequential design based on the z test of a binomial proportion will be used to assess the Safety Endpoint 1. The assumptions and parameters pertaining to this endpoint are as follows:

- Performance Goal: 86% Major EMPOWER MPS System- and Procedure-related CFR through 6 months post-implant
- Attrition: 25% of enrolled subjects through the 6-month visit
- Power = 90%
- Alpha < 2.5% (1-sided)
- Alpha boundary determination: A power error spending function will be used with  $\rho=1.5$

#### • Number of analyses: 2

• Timing of analyses: The single interim endpoint analysis will occur after a minimum of 134 subjects who have undergone any portion of the EMPOWER PG implant procedure have been followed for 6-months (based on a required 0.6 Information Fraction for the interim analysis). The final analysis of this endpoint may occur when 223 subjects who have undergone any portion of the EMPOWER PG implant procedure have been followed for 6-months if the null hypothesis of Safety Endpoint 1 is not rejected at the interim analysis.

Based on these assumptions and parameters, a sample size of 134 subjects is required for the interim analysis with an alpha of 1.2%. If the null hypothesis is not rejected at the interim analysis, a sample size of 223 subjects is required for the final analysis with an alpha of 1.9%.

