#### 11.6.3.2 Assessment of Pooling Across Geographies and Study Sites

The poolability of data by geography and investigational study site will be performed to determine whether there are differences between the US and international geographies, and from study site-to-study site.

Study site-to-study site heterogeneity will be assessed for each endpoint by performing random effects logistic regression analyses. Study sites enrolling 5 subjects or fewer will be combined within region (North America versus other countries) into pooled sites of 6 or more subjects for this pooling analysis.

Study site will be added into the model as a random effect. Study sites will be deemed to be heterogeneous if the variance of the random study site effect is found to significantly differ from zero. A significance level of 15% will be used for each test.

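### Sections 11.6.2 and 11.6.3.2 tie subgroup display and the site heterogeneity label to a 15% test with limited power for safety, so real differences could go unreported

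*Protocol*

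**What the plan says.** Protocol 11.6.2 lists sex, BMI (effectiveness endpoints only), geography, age and race. The method is a regression test: "The subgroup variable will be added to a logistic regression model", followed by "A test for significance at the 15% level will be performed". The display rule comes next: "For each subgroup variable in which a significant difference exists, the results for each subgroup will be presented separately". The section says nothing about variables that are not significant. It adds that the sponsor will not pursue subgroup labeling from these analyses.

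Protocol 11.6.3.2 covers study sites: "Study sites will be deemed to be heterogeneous if the variance of the random study site effect is found to significantly differ from zero", with "A significance level of 15% will be used for each test". Small sites are first merged within region. The section names no estimate, interval or margin, and does not say what follows from a non-significant result.

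Two other places bear on this. Section 11.6.4 carries into the multivariable model only the characteristics found significant. Section 11.1.4.3, by contrast, gives communication success for every posture whatever the pooling test shows.

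SAP 1.4 (Pooling Analysis) is a heading without text in the public copy, so nothing is counted as missing from it.

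**The concern.** The plan's only commitment to show safety by subgroup depends on a significance test, and the safety endpoint has few events. A non-significant result from so few events says little about whether groups differ.

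Two things are at stake. First, a reader of a single-arm approval study may see only the pooled complication-free rate while one group does materially worse. Second, showing differences only when they are significant selects large observed differences, so those shown overstate the truth on average.

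The dataset may be the smaller one. If Safety Endpoint 1 passes at the interim look, section 11.6.1.2 has the effectiveness endpoints tested then as well, with as few as 134 subjects followed to 6 months.

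**Working it through.** **Inputs from the protocol.** Expected 6-month complication-free rate 93%, so 7% complications (synopsis table). Section 11.1.1.2: "Performance Goal: 86% Major EMPOWER MPS System- and Procedure-related CFR through 6 months post-implant", N=134 at the interim and 223 at the final analysis. Test level 15%, sidedness not stated.

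**Assumptions.** Two-sided test. Subgroup shares of 10% to 50% in the higher-risk group, because the documents give none.

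**The plan's own figures reproduce.** Alpha spent at information fraction 0.6 is 0.025 × 0.6^1.5 = 0.0116, stated as 1.2%. The nominal final level is 1.88%, stated as 1.9%. A one-sample z test of 93% against 86% with these two looks reaches 90% power at N=223. Then 0.6 × 223 = 134 and 223/0.75 = 298. The plan states no power for the subgroup or site tests.

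**Expected events.** 0.07 × 134 = 9.4 and 0.07 × 223 = 15.6.

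**Subgroup power.** With share s in the higher-risk group and 7% overall, the lower rate is q = 0.07/(1+s) and the higher rate is 2q. All two-by-two outcomes were enumerated. Power is the summed probability of those whose logistic likelihood-ratio chi-square exceeds 2.07, the 85th percentile on 1 df.

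| Share | Rates at 7% overall | N=134 | N=223 | 12% vs 6%, N=134 | 12% vs 6%, N=223 |
|---|---|---|---|---|---|
| 10% | 6.4% vs 12.7% | 30% | 37% | 29% | 37% |
| 20% | 5.8% vs 11.7% | 35% | 44% | 36% | 45% |
| 30% | 5.4% vs 10.8% | 37% | 48% | 39% | 52% |
| 50% | 4.7% vs 9.3% | 38% | 48% | 44% | 57% |

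**Hand check, 20% share at N=134 (27 vs 107 subjects).** Null SE = √[0.07 × 0.93 × (1/27 + 1/107)] = 0.0550. The test needs an observed difference of about 1.44 × 0.0550 = 0.079. The true difference is 0.0583, with SE √(0.1167 × 0.8833/27 + 0.0583 × 0.9417/107) = 0.0658. Power is about Φ[(0.0583 − 0.079)/0.0658] = 38%, close to the exact 35%. Simulated Wald tests give 27–36% at N=134 and 38–48% at N=223.

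**Exaggeration.** In that case a difference in the true direction is shown only if it is at least about 7.9 points, when the truth is 5.8. At N=223 (45 vs 178) the threshold is 1.44 × √[0.0651 × (1/45 + 1/178)] = 6.1 points, still above 5.8.

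**Other scenarios.**
- A 20% subgroup exactly at the 86% goal: 14% complications, others (0.07 − 0.2 × 0.14)/0.8 = 5.25%. Detected in 51% of trials at N=134 and 66% at N=223.
- 12-month endpoint, 8% overall, doubled rate (normal approximation): 32–38% at N=112 and 41–53% at N=210.
- Relative risk needed for 80% power (normal approximation): about 4.5–6.0 at N=134 and 3.1–3.9 at N=223.

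**Sites, illustration only.** This assumes 18–40 sites after merging and a random-intercept likelihood-ratio test. A doubled rate in 10–50% of sites is flagged in about 9–20% of trials, against a false-positive rate of about 8–11%. A between-site SD of 1.0 on the logit scale is flagged in about 53–77%. The documents fix neither the spread nor the number of enrolling sites, so the point does not rest on these figures.

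**The case against.** The strongest reply is that section 11.6.2 says what happens when a test is significant and stops there. It does not contain the word *only*, does not bar the other results, and does not treat non-significance as consistency. A reader might infer that differences will be hidden as consistency, or that sites passing the test will be treated as poolable. The documents state neither, and the SAP pooling text is not visible. This stands. What remains is that the plan commits to separate safety results for significant variables and to no others.

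A reader might also infer that these tests usually miss a doubled rate at every planned size. The figures do not support that. A balanced split at N=223 with 12% against 6% is detected in 57% of trials, and a 20% subgroup at the performance goal in 51–66%. At 300 subjects the 12% against 6% range is 39–66%.

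Nor do the documents set a power standard for these tests. They are exploratory, they sit outside the success criteria in 11.5.1, and no subgroup labeling is sought. That limits the consequence, but it is no reason to let a p-value decide what is shown.

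Finally, the added estimates will be imprecise. Four events in 27 subjects is 14.8%, with an exact 95% interval of about 4% to 34%. This is true, and the interval tells the reader so, whereas leaving the subgroup out does not.

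**Conclusion.** The point holds as a gap in the reporting rule. Section 11.6.2 commits to separate subgroup results only for variables significant at 15%, and 11.6.3.2 gives a site label from a p-value alone. A doubled 6-month complication rate at 7% overall is detected in about 30–38% of trials at N=134 and 37–48% at N=223; for 12% against 6%, in 29–44% and 37–57%. A real safety difference by sex, age, race or region could therefore go unreported, and those shown will be exaggerated on average.

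These figures assume subgroup shares of 10% to 50% and a two-sided test. The subgroup argument concerns safety, so BMI is outside it. The site part is conditional on what SAP 1.4 contains. No endpoint decision or type I error is affected. This is a cheap improvement.

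**What to change.** In 11.6.2, replace the display sentence with:

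> Event counts, estimates and 95% confidence intervals for each level of every listed subgroup (BMI for effectiveness endpoints only), and for the difference between levels, will be presented regardless of the p-value; a non-significant test will not be taken as evidence of consistency.

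In 11.6.3.2, unless the SAP pooling section already does so, present each endpoint by region with its interval, and the estimated site variance with its interval, alongside the 15% test. The test stays in both sections as a flag.

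The cost is wording and some table rows from models already planned, with no new subjects or data. The downside is that wide intervals and some chance-driven subgroup estimates will be on view, so the tables need a caveat that the analyses are exploratory and imprecise.

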#### 11.6.3 Pooling Analyses

# 11.6.3.1 Assessment of Pooling Across Communication Test Postures

The poolability of the Primary Effectiveness Endpoint 1 data by communication test postures will be performed to determine whether there are differences among the four postures: upright, supine, and right and left side.

Communication test posture heterogeneity will be assessed by performing fixed effects logistic regression analyses. Communication test posture will be added into the model as a fixed effect. Postures will be deemed to be heterogeneous if the variance of the fixed posture effect is found to significantly differ from zero. A significance level of 15% will be used for the test.

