Primary Effectiveness 1	Communication Success between the S- ICD and EMPOWER PG at 6 Month Visit	95%	88%	One-Sided Lower Pointwise Confidence Limit	2.5%	80%	152 tests/ 38 subjects	30%	220 tests/55 subjects
Primary Effectiveness 2	The percent of subjects with an adequate EMPOWER pacemaker PCT measurement.	95%	80%	One-Sided Lower Confidence Limit	2.5%	90%	57	30%	82

3	Tab	ole of C	Contents						
1.	Тіті	TITLE PAGE1							
2	Pro	ROTOCOL SYNOPSIS6							
3	Тав	LE OF C	ONTENTS						
4	Inte	RODUCTI	ION 21						
•	4.1	Backg	round						
5	Dev	ICE DES	CDIDTION 24						
5	5 1	mCRN	A Coordinated System 24						
	5.1	Imnla	n e oor unateu system						
	53	Non-I	ntable Study Devices 24						
		5.3.1	Non-Implantable Study Devices Associated with the EMPOWER System						
		5.3.2	Model 3870 Programmer Software Application and Associated Firmware25						
		5.3.3	Non-implantable Study Devices Associated with the S-ICD System 26						
	5.4	Access	ories						
	5.5	Additi	onal Equipment27						
6	STU	dy Obje	CCTIVES AND ENDPOINTS27						
	6.1	Study	Objectives						
	6.2	Study	Endpoints						
	6.3	Safety	Endpoints						
	6.4	Effecti	iveness Endpoints						
	6.5	Ancill	ary Objectives						
	6.6	Study	Rationale						
7	STU	DY DESI	GN						
	7.1	Scale a	and Duration						
	7.2	Justifi	cation for the Study Design32						
8	SUB.	JECT SE	LECTION						
	8.1	Study	Population and Eligibility33						
	8.2	Inclus	ion Criteria34						
	8.3	Exclus	sion Criteria35						

9	Subj	ECT AC	COUNTABILITY	36
	9.1	Point o	f Enrollment	36
	9.2	Subjec	t Status and Classification	36
		9.2.1	Intent	36
		9.2.2	Attempt	36
		9.2.3	Partial Implant	36
		9.2.4	Implant	37
	9.3	Access mCRM	to EMPOWER MPS Programmer Software and S-ICD System 1 Programming	ı 37
	9.4	Strateg	gies for Recruitment and Retention	37
	9.5	Withd	rawal	38
	9.6	Lost-to	o-Follow-up	39
	9.7	End-of	-Study Definition	39
	9.8	End of	Study Action Plan	39
10	STUI	ру Метн	HODS	40
	10.1	Data C	Collection	40
	10.2	Enroll	ment Visit	42
		10.2.1	Informed Consent	42
		10.2.2	Enrollment Data	42
		10.2.3	Enrollment Visit Source Documentation Requirements	43
	10.3	Implan	ıt	44
		10.3.1	Implant of the EMPOWER PG	44
		10.3.2	Implant of the S-ICD	48
		10.3.3	S-ICD Firmware Update	50
		10.3.4	mCRM Coordinated System Imaging and Testing	51
		10.3.5	S-ICD Evaluation	56
		10.3.6	S-ICD System Programming Considerations	56
		10.3.7	mCRM Coordinated System Data and Source Documentation Requirements	56
	10.4	Pre-Di	scharge Visit	57
		10.4.1	EMPOWER PG Evaluation	58

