## 10.7.3.2 Communication Test

A single Communication Test is required to be performed at the initial programmed Telemetry Setting in each of the four postures noted in **Figure 10-2**. In the event that multiple communication tests are performed within a posture, only the first Communication Test S-ECG Report obtained at the initial programmed Telemetry Setting will serve as the source document for the endpoint. All required testing should be completed in the selected posture before changing to another posture.

In the event of a communication failure in one or more of the four postures during the single test, perform a Communication Threshold Test (described in **Section 10.3.4.5**) in the posture(s) of communication failure. Use the highest value to program the Telemetry Setting output 1 unit above threshold among all tested posture(s). For example, if the threshold is 5, program the output to 6.

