#### 11.1.4.3 Statistical Methods

The analysis for this endpoint will be performed once, either in conjunction with the interim analysis of Safety Endpoint 1, if the analysis of Safety Endpoint 1 is successful in rejecting the null hypothesis, or at the time of the final analysis of Safety Endpoint 1. The analysis for this endpoint will use the communication results taken at the 6 Month Visit and the communication success rate will be calculated using the data from all postures.

A repeated measure logistic regression will be fit with an indicator of communication success of each posture test as the response and subject as the repeated measure in an intercept only model to calculated the adjusted communication success rate and the 97.5% one-sided lower pointwise confidence limit. An unstructured correlation matrix will be used, unless a different structure is found to be more appropriate. The adjusted communication success rate and the 97.5% one-sided lower pointwise confidence limit by converting the intercept estimate and 97.5% one-sided upper pointwise confidence limit from the model previously described into an event rate and corresponding confidence limit. This adjusted 97.5% one-sided lower pointwise confidence limit of the communication success rate will compared to the performance goal of 88%. If the lower confidence limit exceeds 88%, the null hypothesis will be rejected. Please see the Statistical Analysis Plan (SAP) for more specifics. The unadjusted rate and 97.5% one-sided lower pointwise confidence limit and 97.5% one-sided using the one-sided Score methodology will also be presented as sensitivity analysis.

A subject-level evalution of the communication success rate across the four postures is being analyzed as an ancillary objective. See **Section 11.2**.

Missing posture testing data due to missed 6 Month Visits or a missing posture of the 4 tested will be considered missing data. To assess the potential impact missing data could have had on the analysis results, a tipping point analysis will be conducted. The tipping point analysis will assign each missing posture test as either a failure or success. All possible combinations of these posture tests' data will be evaluated along with the actual observed data to find the point, if any, at which the endpoint is failed.

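### The posture poolability test in Section 11.6.3.1 names no within-subject term; if run as an ordinary logistic regression at 134 to 223 subjects, its 15% level is conservative when results within a subject are positively correlated (minor)

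*Protocol*

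**What the plan says.** Posture is a within-subject factor by design. At the 6 Month Visit, Protocol Section 10.7.3.2 states: "A single Communication Test is required to be performed at the initial programmed Telemetry Setting in each of the four postures".

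The primary analysis in Section 11.1.4.3 respects this. It is a repeated-measures logistic regression with "each posture test as the response and subject as the repeated measure in an intercept only model". On the correlation it says only: "An unstructured correlation matrix will be used, unless a different structure is found to be more appropriate". No value is given or assumed.

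Section 11.1.4.3 also promises a success rate for each posture and an assessment of poolability across postures. Section 11.6.3.1 describes that assessment: "Communication test posture heterogeneity will be assessed by performing fixed effects logistic regression analyses". It continues: "Communication test posture will be added into the model as a fixed effect", and "A significance level of 15% will be used for the test". It does not say which model is meant, and it names no subject, repeated or matching term. Its criterion for heterogeneity is that the variance of the posture effect differs from zero.

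SAP Section 1.4 (Pooling Analysis) shows a heading with no visible text, so it cannot settle the question.

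**The concern.** Section 6.6 explains that communication can depend on how the two devices are oriented to each other, and that posture is varied for this reason. The poolability test is the planned formal check that one pooled rate is a fair summary of the four postures. A 15% level suggests that a sensitive screen was wanted.

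An ordinary logistic regression would treat the four results of one subject as if they came from four separate groups. For a factor that varies between subjects, ignoring clustering usually makes a test too liberal. For a factor that varies within subjects the direction reverses. Positive correlation makes posture contrasts more precise, the ordinary model does not see this, and its test becomes conservative. At stake is a formal finding of homogeneity that the test had less chance of contradicting than its stated level implies.

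**Working it through.** **Inputs.** Expected success 95% (Synopsis table); goal 88%, one-sided 2.5%, power 80%, attrition 30% (Section 11.1.4.2); four postures per subject (10.7.3.2); poolability level 15% (11.6.3.1); 134 subjects at the interim and 223 at the final Safety Endpoint 1 analysis (11.1.1.2), which set the timing of this endpoint. Those two counts are before missing tests and before subjects without both devices. The within-subject correlation r is an assumption, shown from 0 to about 0.5.

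**The plan's own figure.** The poolability test has no stated sample size or power. The endpoint's sample size does reproduce:

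- n = [(1.96·√(0.88·0.12) + 0.842·√(0.95·0.05)) / 0.07]² = 137.3.
- With continuity correction: (137.3/4)·[1 + √(1 + 2/(137.3·0.07))]² = 151.3, rounded up to 152 tests = 38 subjects × 4.
- Attrition: 38/0.70 = 54.3, rounded up to 55 subjects, × 4 = 220 tests.

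**Large-sample level of the ordinary test.** With a common rate p, the variance of a difference between two postures is 2p(1−p)(1−r)/n. The ordinary model uses 2p(1−p)/n. Its 3-df statistic therefore behaves as (1−r) times a chi-square on 3 df. The 15% critical value is 5.317, so the true level is P(χ²₃ > 5.317/(1−r)):

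| r | 5.317/(1−r) | true level |
|---|---|---|
| 0 | 5.32 | 15.0% |
| 0.1 | 5.91 | 11.6% |
| 0.2 | 6.65 | 8.4% |
| 0.3 | 7.60 | 5.5% |
| 0.4 | 8.86 | 3.1% |
| 0.5 | 10.63 | 1.4% |

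**Simulated level.** Exchangeable correlated binary data, 8,000 runs per setting, all postures at 95%, 134 subjects. The ordinary likelihood-ratio test rejects about 16%, 12 to 13%, 9.5%, 5% and 2% of the time at r = 0, 0.10, 0.21, 0.36 and 0.53. Cochran's Q, which is matched on subject, stays at 14 to 15%. A GEE Wald test with subject as cluster (600 runs) gives 12 to 14% for r from 0 to 0.36.

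**Chance of flagging a worse posture.**

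| Setting | Subjects | Ordinary LR | Cochran's Q |
|---|---|---|---|
| 90% vs 96%, r about 0.35 | 134 | 71% | 87% |
| 90% vs 96%, r about 0.35 | 223 | 91% | 98% |
| 90% vs 96%, r about 0.10 | 223 | 89.6% | 92.0% |
| 88% vs 97%, r about 0.32 | 134 | 97% | 99% |
| 88% vs 97%, r about 0.32 | 223 | about 100% | about 100% |

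For the first row, the Wald versions give 66% for the ordinary model and 83% for GEE. The 6-point deficit is therefore missed 29% of the time by the ordinary likelihood-ratio test, against 13% (Cochran's Q) or 17% (GEE). For 88% against 97%, the ordinary test flags about 95% or more at every correlation tried. The generalised score test proposed below was not itself simulated; the GEE figures are for the Wald form.

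**At the 38-subject minimum.** Sparse failures change the picture. The likelihood-ratio test is liberal at low correlation (23% at r = 0, 19% at 0.10), about nominal at 0.20 (14.5%) and conservative only above that. The ordinary Wald test rejects 1% or less even at r = 0, because some posture has no failures in 33 to 47% of runs.

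**The case against.** The strongest reply is that Section 11.6.3.1 may already mean the right thing. Adding posture to the model could refer to the only model specified for this endpoint, the intercept-only repeated-measures model of 11.1.4.3. On that reading, fixed effect describes only how posture enters, in contrast to the random site and sheath effects of 11.6.3.2 and 11.6.3.3. This stands as a possible reading, and SAP 1.4 might confirm it. It is the less plain one: where the protocol wants a repeated or random term, it says so.

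Three stronger inferences are tempting, and the documents do not support them.

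- **That a poor posture would be hidden.** Section 11.1.4.3 presents the rate for each posture whatever the test shows, and Section 11.2 adds a summary of how many postures succeed per subject. A posture at the 88% goal, with 97% elsewhere, would almost always be flagged at 134 or 223 subjects. The loss concerns moderate deficits.
- **That the test is conservative without condition.** This needs positive correlation and adequate numbers. At correlation 0.1 with 134 subjects the loss is only about 2 points of level, and at 38 subjects with low correlation the likelihood-ratio test errs the other way.
- **That the primary result is compromised.** The comparison with 88% does not depend on the poolability test, and the visible text attaches no action to a heterogeneous finding.

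Nor can the plan be faulted for an empty SAP 1.4, since its text may simply not be visible in the public copy.

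**Conclusion.** The point holds as a minor one. The visible wording of 11.6.3.1 does not account for the matching of postures within subject, although the primary model does. If it is carried out as an ordinary logistic regression at 134 to 223 subjects, positive correlation pushes the 15% test below its stated level. The shortfall is about 3 points at correlation 0.1, 7 at 0.2 and nearly 10 at 0.3. At correlation about 0.35 and 134 subjects it also costs 16 to 17 points of power for a 90% against 96% deficit.

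This rests on the ordinary-regression reading, on an assumed exchangeable correlation for which the documents give no figure, and on nearly all of the 134 or 223 subjects having four posture results. Positive correlation is plausible, because the four tests share one subject, one pair of implanted devices and one programmed Telemetry Setting, but its size is unknown.

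The sentence needs repair on any reading. For a fixed effect, a variance that differs from zero is not a defined test quantity; the phrase matches the random-effects wording of the two following subsections. Section 11.1.4.3 also sends the reader to Section 11.7.3 for the pooling analysis, while the text stands in 11.6.3.

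**What to change.** In Section 11.6.3.1:

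- State that posture is added as a 3-df fixed effect to the repeated-measures logistic model of Section 11.1.4.3, with subject as the repeated measure, and tested with a generalised score test at the 15% level.
- Name Cochran's Q, on subjects with all four postures, as the test when a posture has few or no failures, and set in advance the failure count that triggers it.
- Replace the variance criterion with this 3-df test, and correct the cross-reference in 11.1.4.3.
- If SAP 1.4 already specifies such an analysis, align 11.6.3.1 with it.

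The cost is a few sentences and one added term in a model that is already being fitted. No new data are needed and the primary test does not change. With positive correlation, posture differences will be flagged more often, at about the rate that the 15% level already promises.
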